9.5. Interim analysis to monitor study progress

Interim reports will be prepared twice yearly until the final analysis has been completed. In general, reports will describe accrual, projected completion date, pre-treatment characteristics of patients, and frequency and severity of adverse events.

10. Study Timelines

Task	Year 1		Year 2	
Enroll 34 patients and deliver 4D CT ventilation image-guided personalized radiotherapy				
Assess the safety/feasibility of 4D CT ventilation image-guided personalized radiotherapy				
Estimate the clinical significance of 4D CT ventilation image-guided personalized radiotherapy				

11. Patient Assessments

11.1. Pre-treatment assessments

Staging workup will include PET/CT, MRI of the brain (this is only required for locally advanced patients and for other patients, it is optional), and CT of the chest and upper abdomen performed with contrast (recommended, but not required) within 8 weeks prior to registration, as well as histologic or cytologic documentation of lung cancer. PFT to include routine spirometry, lung volumes, and diffusing capacity should be performed within 8 weeks before treatment. CBC with differential and comprehensive metabolic panel will be obtained within 14 days of enrollment to ensure adequate marrow reserve and end organ function.

11.2. Evaluation during treatment

In an effort to improve the capture and consistency of AE reporting, essential AEs commonly associated with lung cancer radiotherapy, including but not limited to esophagitis, pneumonitis, pericarditis, dermatitis, hematologic toxicity, and chest wall pain are to be assessed at baseline and weekly during treatment using the NCI-CTCAE version 4.0. Additional AE terms and grading criteria can be accessed online at <http://ctep.cancer.gov/reporting/ctc.html>. Guidelines for management of AEs are outlined in section 7. History, physical examination, Zubrod performance status, and body weight will also be obtained weekly during treatment.

11.3. Discontinuation of protocol treatment

Protocol treatment may be discontinued for any of the following reasons:

- Progression of disease
- Unacceptable adverse events [at the discretion of the treating physician(s)]
- Patient refusal
- If protocol treatment is discontinued, follow-up and data collection will continue as specified.

11.4. Post-treatment evaluations

In an effort to improve the capture and consistency of AE reporting, essential AEs commonly associated with lung cancer radiotherapy, including esophagitis, pneumonitis, pericarditis, dermatitis, hematologic toxicities, spinal cord injury, chest wall pain, and are to be assessed at follow-up every 3 months for a minimum of **2 years after treatment using the NCI-CTCAE version 4.0.** Additional AE terms and grading criteria can be accessed online at <http://ctep.cancer.gov/reporting/ctc.html>. Post-treatment PFTs will be performed at 6 months post-treatment, to include routine spirometry, lung volumes, diffusing capacity and diffusing capacity.

Disease response and progression will be monitored by the use of contrast-enhanced CT of the chest every 3 months for the first 2 years post-treatment. PET/CT will be obtained at the discretion of the treating physician or to follow up suspicious findings on CT. Patient assessments are outlined in Appendix III.

11.5. Discontinuation of follow-up assessments

Follow-up assessments may be discontinued for either of the following reasons:

- Patient refusal
- Patient's withdrawal of consent; Data for these patients will not be used for analysis.
- Otherwise, patients will be followed at least every three months for two years following treatment.

12. Ethical and Regulatory Considerations

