7.2. Adverse Event Definitions

Adverse Events (AEs)

Any unfavorable and unintended sign (including an abnormal laboratory finding), symptom, or disease temporally associated with the use of a medical treatment or procedure regardless of whether it is considered related to the medical treatment or procedure (attribution of unrelated, unlikely, possible, probable, or definite).

Serious Adverse Events (SAEs)

Any adverse experience occurring during any part of the protocol treatment and 30 days after that results in any of the following outcomes:

- Results in death.
- Is life-threatening (refers to an AE in which the patient was at risk of death at the time of the event. It does not refer to an event which hypothetically might have caused death if it were more severe).
- Requires inpatient hospitalization or prolongation of an existing hospitalization
- Results in persistent or significant disability or incapacity. (Disability is defined as a substantial disruption of a person's ability to conduct normal life functions).
- Is a congenital anomaly/birth defect.
- Is a medically important event. This refers to an AE that may not result in death, be immediately life threatening, or require hospitalization, but may be considered serious when, based on appropriate medical judgment, may jeopardize the patient, require medical or surgical intervention to prevent one of the outcomes listed above, or involves suspected transmission via a medicinal product of an infectious agent.

Intensity (Severity) of the Adverse Event

The intensity or severity of AEs will be graded according to the NCI-CTCAE version 4.0 criteria.

Adverse Event Documentation

All AEs occurring after the subject has received the first dose of investigational treatment will be fully recorded in the subject's case record form. Documentation will be supported by an entry in the subject's file. Each event will be described in detail along with start and stop dates, severity, relationship to study treatment, action taken and outcome.

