9.2. Patient accrual

We aim to accrue 34 patients over 1.5 years. Patient accrual will continue until either the projected sample of 34 patients has been enrolled, or the number of patients developing Grade ≥ 3 AEs or drop-out due to intolerance of treatment exceeds five. Patient follow-up will continue until all patients have at least two years of follow-up, to allow for assessment of longer-term AEs.

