9.3. Analysis plan

Primary endpoints: (1) Grade ≥ 3 radiation pneumonitis, (2) grade ≥ 3 esophagitis, (3) other grade ≥ 3 AEs that occur ≤ 12 months after treatment and drop-out defined as definitely, probably, or possibly related to the protocol treatment.

We will estimate the rates of AEs and tolerability with exact 95% confidence intervals. 4D CT ventilation image-guided personalized radiotherapy will be considered safe if AE rates are lower than the following acceptable rates (determined based on the published toxicity data for locally advanced lung cancer patients): (1) grade ≥ 3 radiation pneumonitis, 13% (Jiang *et al.*, 2012), (2) grade ≥ 3 esophagitis, 21% (Wei *et al.*, 2006), and (3) other grade ≥ 3 AEs and drop-out, 20% (Bradley *et al.*, 2015).

Secondary endpoints

Analyses of secondary endpoints will be primarily descriptive rather than hypothesis testing.

Toxicity will be summarized by frequency and exact 95% confidence intervals, overall and separately by grade and organ system.

The clinical significance of 4D CT ventilation image-guided personalized radiotherapy will be estimated by evaluating: (1) clinical and subclinical endpoints for pulmonary toxicity (including radiation pneumonitis, PFTs, 6-min walk test, and BODE index); (2) correlation between those endpoints and functional dose-volume parameters. Radiation pneumonitis will be assessed at follow-up every 3 months for a minimum of 2 years after treatment using the NCI-CTCAE version 4.0. Post-treatment changes in PFTs (including spirometry, lung volumes and diffusing capacity), 6-min walk test, and the BODE index will be evaluated at the time of 6-month follow-up. Using composite treatment plans, the following lung functional dose-volume parameters will be calculated: functional mean lung dose (fMLD), functional V_{20} (fV_{20}) and functional effective dose (fD_{eff}) (Vinogradskiy *et al.*, 2013), which will be correlated with the endpoints for pulmonary toxicity.

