9.4. Sample size

We will examine the safety of 4D CT ventilation image-guided personalized radiotherapy based on AEs during the first 12 months of follow-up and toxicity-related drop-out. With a sample size of 34 patients, we will be able to see grade ≥ 3 radiation pneumonitis, grade ≥ 3 esophagitis and other grade ≥ 3 AEs at least once with 94%, 99% and 99% probabilities, respectively, assuming

true rates of 13%, 21% and 20%, respectively. We can also estimate these AE rates with a standard error of 8%, 9% and 9%, respectively.

Approximately 37% of patients are estimated to die over the first 12 months of follow-up according to the published survival data for patients with locally advanced NSCLC (Machtay *et al.*, 2012). Also 1% of patients are estimated to drop out for reasons unrelated to the protocol treatment. To compensate for possible loss of patients for such reasons, a sample size of 34 (increased by 38% from 20) will be used.

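### Section 11.5 excludes patients who withdraw consent from analysis without exempting toxicity already recorded, so primary safety events can be missing from the final rates (minor)

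*Combined protocol and SAP*

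**What the plan says.** Section 11.5 gives two reasons for stopping follow-up assessments. Refusal by the patient carries no rule about data. Withdrawal of consent does: "Data for these patients will not be used for analysis".

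Section 9.3, repeating 9.1, defines three primary endpoints: grade 3 or higher pneumonitis, grade 3 or higher esophagitis, and other grade 3 or higher events within 12 months together with "drop-out defined as definitely, probably, or possibly related to the protocol treatment". The treatment "will be considered safe if AE rates are lower than the following acceptable rates", which are 13%, 21% and 20%. Section 9.4 likewise rests the safety assessment on adverse events and "toxicity-related drop-out".

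Three other places bear on the point:

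- Section 7.2: "All AEs occurring after the subject has received the first dose of investigational treatment will be fully recorded" in the case record form.
- Section 9.2: accrual ends early if the number of patients with grade 3 or higher events or "drop-out due to intolerance of treatment exceeds five".
- Section 11.3: patients who stop protocol treatment remain in follow-up and data collection.

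**The concern.** Drop-out related to treatment is itself a primary outcome. A patient who has severe toxicity, leaves because of it and formally withdraws consent counts as an event under 9.3 and is removed under 11.5. The documents do not say which rule prevails.

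If toxicity prompts the withdrawal, the exclusion depends on the outcome. Removing such a patient takes one from the numerator and one from the denominator, which lowers the rate of every component in which that patient had an event. The verdict compares these rates with fixed upper limits, so the error runs in the direction that favours the treatment.

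**Working it through.** **1. What the text covers.** The sentence in 11.5 refers to the patients' data without a time limit. Section 9.3 names no analysis population that would override it. Section 11.3 deals with stopping treatment, not with withdrawing consent. Section 12.2 ties consent to institutional, NCI and Federal regulations but does not say what happens to data collected before withdrawal. Nothing in the documents narrows the sentence.

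**2. Which denominator.** Section 9.4 states "a sample size of 34 (increased by 38% from 20) will be used". It gives probabilities of at least one event of 94%, 99% and 99%, and standard errors of 8%, 9% and 9%. With 1 − (1 − p)^n and √(p(1 − p)/n) at p = 13%, 21% and 20%:

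- n = 20: 93.8%, 99.1%, 98.8%; standard errors 7.5%, 9.1%, 8.9%. These match the plan.
- n = 34: 99.1%, 99.97%, 99.95%; standard errors 5.8%, 7.0%, 6.9%. These do not match.

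The plan's precision therefore belongs to about 20 evaluable patients, and both denominators are used below.

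**3. One or two deletions, point-estimate reading.** The rate moves from x/n to (x − d)/(n − d), where d is the number of patients with an event who are removed. Each row starts at the smallest x that is not below the limit.

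| Endpoint (limit) | n | All data | One removed | Two removed |
|---|---|---|---|---|
| Pneumonitis (13%) | 34 | 5/34 = 14.7% | 4/33 = 12.1% | – |
| Pneumonitis (13%) | 20 | 3/20 = 15.0% | 2/19 = 10.5% | – |
| Other AEs and drop-out (20%) | 20 | 4/20 = 20.0% | 3/19 = 15.8% | – |
| Esophagitis (21%) | 20 | 5/20 = 25.0% | 4/19 = 21.1% | 3/18 = 16.7% |

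One deletion reverses the verdict for pneumonitis and for other AEs and drop-out; esophagitis needs two. The exact 95% intervals hardly move: 5.0–31.1% for 5/34 and 3.4–28.2% for 4/33.

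**4. Average effect.** Model: X ~ Bin(n, p) with p equal to the limit; each patient with an event withdraws consent with probability w, so D | X ~ Bin(X, w); the verdict is taken on (X − D)/(n − D). The values of w are assumptions. Only patients with an event withdraw, which is the most adverse pattern. The accrual stop is ignored.

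Chance of a rate below the limit, point estimate:

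| Endpoint | n | w = 0 | 1% | 2% | 10% |
|---|---|---|---|---|---|
| Pneumonitis | 34 | 54.2% | 55.1% | 56.0% | 63.3% |
| Esophagitis | 34 | 57.6% | 57.6% | 57.8% | 61.1% |
| Other AEs and drop-out | 34 | 46.6% | 47.8% | 49.0% | 58.5% |
| Pneumonitis | 20 | 50.8% | 51.5% | 52.2% | 58.0% |
| Esophagitis | 20 | 58.6% | 58.6% | 58.7% | 60.3% |
| Other AEs and drop-out | 20 | 41.1% | 42.0% | 42.9% | 50.3% |

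The largest shift at w = 2% is 48.96 − 46.61 = 2.35 points; at w = 10% it is 58.47 − 46.61 = 11.9 points.

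If instead the upper exact 95% confidence limit must lie below the acceptable rate, the largest shift at w = 10% is 3.06 − 1.64 = 1.4 points (esophagitis, n = 34).

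**5. Accrual stop.** More than five affected patients ends accrual. At n = 34 and true rates at the limits, one component alone exceeds five with probability 75% (esophagitis) or 70% (other AEs and drop-out). Those n = 34 rows often describe trials that 9.2 may have cut short. Five affected patients, as in the 5/34 example, do not trigger the stop.

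**The case against.** The strongest case on the other side has four parts.

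- **Reach.** Only formal withdrawal of consent is affected. Patients who stop treatment stay under observation (11.3), and refusal of follow-up carries no exclusion. This stands.
- **Record.** Events before withdrawal are recorded (7.2), serious events are followed up (Section 7.3), and twice-yearly reports describe adverse events (9.5). A reader might infer that toxicity disappears from the trial. The documents do not support that: 11.5 governs analysis, so what can be lost is the event's place in the final rates.
- **Size.** The examples are knife-edge cases. At a true rate equal to the limit, the counts 5/34, 3/20 and 4/20 have probabilities of about 18%, 23% and 22%, and a patient with an event must then also withdraw. The 4/20 case is a tie with its limit. No withdrawal rate is given; the figure in 9.4, that "1% of patients are estimated to drop out for reasons unrelated to the protocol treatment", concerns a different group. This stands and holds the severity to minor.
- **Consent form.** It was not available for review. It may already allow retention, or it may require deletion. The sentence may also have been meant only for data after withdrawal, since it sits in a section on stopping assessments, but it does not say so. This makes the fix conditional; it does not remove the conflict.

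A reader might also infer that the accrual stop either is or is not affected. The documents do not say whether withdrawn patients count toward it, so neither reading is supported.

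**Conclusion.** The conflict is real. Followed literally, 11.5 removes recorded toxicity and related drop-outs that 9.1, 9.3 and 9.4 count as primary outcomes, and where toxicity leads to withdrawal the bias favours a safe verdict. This is a stated rule that can give a wrong result, not merely missing detail.

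The expected effect is small. It stays within about 2.4 points in the chance of a safe verdict for 1–2% withdrawal among patients with an event on the point-estimate reading, and within 1.5 points even at 10% on the upper-bound reading. Section 9.3 does not say which reading applies. These sizes rest on assumed withdrawal probabilities, true rates at the limits and no accrual stop. A reader might conclude that the safety verdict is likely to be wrong; the documents give no withdrawal rate to support that. Severity: minor.

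**What to change.** Replace the sentence in 11.5 with: *No further data are collected after withdrawal of consent; data collected up to withdrawal, including adverse events, are retained and analysed as far as the consent terms allow, and a withdrawal at least possibly related to protocol treatment counts as drop-out under endpoint (3).*

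Add one line to 9.3: where the consent terms require deletion, report the number of patients removed, with a worst-case sensitivity analysis that counts each of them as an event (for example, 4/33 = 12.1% with one patient removed becomes 5/34 = 14.7%).

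Cost: two short text changes, with no new data collection and no change in sample size. The change does return withdrawn patients to the analysis population and may make the observed rates slightly less favourable. It may also need a matching line in the consent form.

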12.1. Ethical conduct of the study

This study will be conducted in accordance with the Declaration of Helsinki and Good Clinical Practice (GCP) according to (International Conference on Harmonization) ICH guidelines. Specifically, the study will be conducted under a protocol reviewed by the IRB; the study will be conducted by scientifically and medically qualified persons; the benefits of the study are in proportion to the risks; the rights and welfare of the subjects will be respected; the physicians conducting the study do not find the hazards to outweigh the potential benefits; and each subject will give his or her written, informed consent before any protocol-driven tests or evaluations are performed.

Essential clinical documents will be maintained to demonstrate the validity of the study and the integrity of the data collected. Master files will be established at the beginning of the study, maintained for the duration of the study and retained according to the appropriate regulations.

12.2. Informed consent procedures

Informed consent will be obtained before conducting any study-specific procedures (*i.e.*, all of the procedures described in the protocol). The process of obtaining informed consent will be documented in the patient source documents.

All patients will have signed an informed consent for participation in research activities in accordance with all institutional, NCI and Federal regulations, and will have been given a copy of the Experimental Subject's Bill of Rights.

12.3. Protocol deviations

PI, [name] and Co-PI, [name] will discuss all protocol waivers and/or treatment deviations immediately, and will submit an amendment to the protocol if the deviation is likely to occur again. All protocol deviations will be reported in accordance with UCD IRB Administration and UCD Cancer Center policies.

13. Data Safety and Monitoring

In addition to the requirements for AE reporting as outlined in section 7, this protocol is also subject to the UC Davis Cancer Center's (UCDCC) Data and Safety Monitoring Plan. The UCDCC is committed to pursuing high-quality patient-oriented clinical research and has established mechanisms to ensure both scientific rigor and patient safety in the conduct of clinical research studies. The UCDCC relies on a multi-tiered committee system that reviews and monitors all cancer clinical trials and ensures the safety of its participants, in compliance with institutional and federal requirements on AE reporting, verification of data accuracy, and adherence to protocol eligibility requirements, treatment guidelines, and related matters. The Scientific Review Committee (SRC) assumes overall oversight of cancer studies, with assistance and input from two independent, but interacting, committees: the Quality Assurance Committee and the Data Safety Monitoring Committee. A multi-level review system strengthens the ability of the UCDCC to fulfill its mission in conducting high quality clinical cancer research.

14. Data Sharing

The anonymized pre- and mid-treatment CT image data acquired in this study will be shared with external investigators upon request for other research activities. To date we have received a request from [name] (University Medical Center Hamburg-Eppendorf, Germany) who will develop a repeat 4D CT image database that will be publicly accessible for various developments and investigations such as respiratory motion modeling. Anonymized CT image data will be transferred through cloud-based secure file sharing, e.g., Box (<https://ucdavis.app.box.com>).

15. Potential Benefits to Subjects

Potential benefits from this study include a potentially lower risk to experience pulmonary toxicity by 4D CT ventilation image-guided personalized radiotherapy compared to standard anatomic image-guided radiotherapy. However, there is no guarantee that the patient will benefit directly from participating in this study.

16. Economic Burden to Subjects

There will be no additional costs to subjects because of participation in this study.

17. Sharing of Results with Subjects

The results of this study will not be shared with subjects or subjects' primary care physicians.

18. Devices

In vivo EPID dosimetry with the PerFRACTION software calculates the dose of the day reconstructed from EPID measurements in patient anatomy using the treatment plan CT image data. The calculated dose of the day will be compared with the plan dose to estimate changes in patient anatomy. The performance of in vivo EPID dosimetry will be evaluated by comparing the PerFRACTION analysis results with the dose of the day calculated with the mid-treatment CT image data as reference. This device poses no additional risk to subjects.

REFERENCES

Abratt R P, Willcox P A and Smith J A 1990 Lung cancer in patients with borderline lung functions--zonal lung perfusion scans at presentation and lung function after high dose irradiation *Radiother Oncol* **19** 317-22

- Bradley J, Graham M V, Winter K, Purdy J A, Komaki R, Roa W H, Ryu J K, Bosch W and Emami B 2005a Toxicity and outcome results of RTOG 9311: a phase I-II dose-escalation study using three-dimensional conformal radiotherapy in patients with inoperable non-small-cell lung carcinoma *Int J Radiat Oncol Biol Phys* **61** 318-28
- Bradley J D, Graham M, Suzanne S, Byhardt R, Govindan R, Fowler J, Purdy J, Michalski J, Gore E and Choy H 2005b Phase I results of RTOG L-0117; a phase I/II dose intensification study using 3DCRT and concurrent chemotherapy for patients with Inoperable NSCLC *J Clin Oncol* **23** 7063 (Abstract)

APPENDIX I:

ZUBROD PERFORMANCE SCALE

- 0 Fully active, able to carry on all pre-disease activities without restriction (Karnofsky 90-100).
- 1 Restricted in physically strenuous activity but ambulatory and able to carry work of a light or sedentary nature. For example, light housework, office work (Karnofsky 70-80).
- 2 Ambulatory and capable of all self-care but unable to carry out any work activities. Up and about more than 50% of waking hours (Karnofsky 50-60).
- 3 Capable of only limited self-care, confined to bed or chair 50% or more of waking hours (Karnofsky 30-40).
- 4 Completely disabled. Cannot carry on self-care. Totally confined to bed or (Karnofsky 10-20).
- 5 Death (Karnofsky 0).

